The Effect of Glasthma Syrup in Asthma: a study protocol for a triple-blind randomized controlled trial

[name]¹, [name]^{2*}, [name]³, [name]⁴, [name]⁵, [name]¹, [name]⁶, [name]⁷, [name]⁷

¹School of Persian and Complementary Medicine, Mashhad University of Medical Sciences, Mashhad, Iran

²Social Determinants of Health Research Center, Health School, Mashhad University of Medical Sciences, Mashhad, Iran

³Department of Community Medicine and Public Health, Faculty of Medicine, Mashhad University of Medical Sciences, Mashhad, Iran

⁴Lung Disease Research Center, Faculty of Medicine, Mashhad University of Medical Sciences, Mashhad, Iran

⁵Department of Internal Medicine, Faculty of Medicine, Islamic Azad University-Mashhad Branch, Mashhad, Iran

⁶Department of Immunology and Allergy, Head of Allergy Research Center, Ghaem Hospital, Mashhad University of Medical Sciences, Mashhad, Iran

⁷Student Research Committee, Mashhad University of Medical Sciences, Mashhad, Iran

Received January 24, 2022

Reviewed February 4, 2022

Accepted July 28, 2022

*Corresponding Author

[name]
Social Determinants of Health Research
center, Health School, Mashhad
University of Medical Sciences, [name],
Iran
[contact]
E-mail: [contact]

Objectives: Asthma is a chronic disease, and the demand for herbal medicines in this field has increased in recent years. The new findings highlight the role of the gut-lung axis in the pathophysiology of asthma. Hence, this study will evaluate the safety and efficacy of Glasthma syrup, an herbal formula based on Persian medicine, in improving asthma and regulating intestinal permeability. The formula consists of five herbal ingredients that have anti-inflammatory effects on the respiratory tract, also known as gut tonics.

Methods: The study will be conducted as a placebo-controlled, triple-blind, randomized trial. It will consist of a 4-week intervention followed by a 4-week follow-up period. The target sample size is 20 patients with moderate asthma aged 18 to 60 years. Eligible participants will be randomly assigned to either the experimental group or the control group in equal numbers. Patients in the experimental group will take Glasthma syrup (7.5 mL, twice a day), while patients in the control group will take a matching placebo. Both groups will receive a 4-week combination of a long-acting beta2 agonist and a leukotriene modulator as standard of care. Inhaled corticosteroids can be used as rescue medication as needed.

Results: The primary outcomes are asthma symptom scale, lung function, and intestinal permeability. Secondary outcomes include quality of life, symptom recurrence rates, and blood tests. A safety assessment will also be conducted during the trial.

Conclusion: In this trial, the effects of Glasthma syrup in patients with moderate asthma will be examined. The study will also assess the effects of the formulation on the gut-lung axis by simultaneously monitoring the gut permeability index, asthma symptoms, and lung function.

Keywords: bronchial asthma, persian medicine, intestinal permeability, clinical trial

INTRODUCTION

In Persian medicine, the treatment of asthma with herbs has been mentioned in various formulas [1]. Despite the rich variety of medicinal preparations in Persian medicine, there has been limited research on their effectiveness and possible

adverse effects [2-6]. Considering the increasing popularity of herbal and traditional remedies, it is necessary to evaluate the performance of these herbal therapeutic formulations and their side effects [7].

Asthma is a chronic disease, and multiple medications have been developed to reduce inflammation of the airways and con-

tract the smooth muscles of walls.

Common drugs for asthma contain, as active ingredients, medicinal plants mentioned in some traditional medicine recipes [8]. Physiologic effects such plants varies depending on the composition of each formulation.

This complexity is not fully understood, but empirical evidence suggests that they have a measurable effect on mucus accumulation, improve bronchial relaxation, and reduce airway inflammation [9].

According to Persian medical theory, the function of the gastrointestinal tract affects the incidence and severity of diseases of other organs and systems, such as the respiratory system. In recent years, several studies have confirmed the gut-lung axis theory [10-13].

Under the theory of the relationship between the gastrointestinal tract and the respiratory system, it seems that controlling nonspecific gastrointestinal malabsorption can greatly reduce the incidence and severity of asthma. In support of this theory, there are several formulations in the Persian medical literature that control respiratory symptoms using supplements that affect the gastrointestinal tract [14-17].

To test this theory, we designed an herbal formula comprising five herbal substances that have tonic effects on both the lungs and the gut: licorice root (*Glycyrrhiza glabra*), *Echium amoenum* flower, date fruit (*Ziziphus jujuba*), *Cydonia oblonga* fruit (papaya), and hazelnut.

Licorice root is the basis of this recipe. This herb improves gastrointestinal function and breathing, and it also has an anti-inflammatory effects [8].

Echium amoenum is used as a herbal tea for bronchitis, chronic coughs, asthma flare-up symptoms, and as a general tonic [17]. Some of its compounds (gamma-linoleic acid) has antioxidant effects [18-21].

Jujube fruit is a dietary supplement that contains high levels of bioactive compounds such as dietary fiber, minerals, and natural antioxidants. It induces a protective effect in IBD by improving intestinal barrier function [9].

Cydonia oblonga has anti-inflammatory and antioxidant properties [22]. It has been reported to show gastrointestinal benefits in gastroesophageal reflux disorder, gastritis, and colitis [23, 24].

Hazelnut was introduced specifically as a gut tonic for its antitussive properties [25], modulatory effects on the gut microbiom [26], and anti-inflammatory, antioxidant, and metabolic effects on the heart [27].

The aim of this study is to evaluate the efficacy and safety of this formulation (Glasthma syrup) on asthma symptoms, lung function test parameters, and intestinal permeability indices.

MATERIALS AND METHODS

1. Study registry

This is a single-center randomized triple-blind controlled trial. The trial was authorized at the Medical University of Mashhad, Iran (code: 991551), approved by the Iranian National Biomedical Research Ethics Committee, code IR.MUMS.REC.1400.076, and registered with the Iranian Clinical Trials Registry.

The goal of the trial is to analyze the effect of Glasthma syrup, compared with placebo, on respiratory symptoms, pulmonary function test results, and gut permeability index (lactulose/mannitol ratio) in patients with moderate asthma. This study complies with the Standard Protocol Item: Guidelines for Interventional Trials (SPIRIT) Recommendations (Table 1).

2. Trial procedure

The complete trial includes a screening assessment, a 1-week run-in period, a 4-week treatment period (weeks 1 to 4), and a 4-week follow-up period (weeks 5 to 8) (Fig. 1).

First, patients with asthma who met the inclusion criteria will be invited to participate in the study. They will be given the necessary explanations about the study conditions, and if they agree, after signing a written consent form, an asthma registry questionnaire will be completed [28]. The patients will have a complete blood count (CBC), liver and kidney function tests, total serum IgE test, pulmonary function test (PEF), urine analysis, creatinine clearance (ClCr), and a 5-hour urine L:M test.

After the baseline assessment, participants will be randomly assigned to receive Glasthma syrup or placebo syrup for 4 weeks. Symptom severity and quality of life will be self-assessed by participants and recorded weekly throughout the treatment period. Face-to-face blind assessments will be scheduled for the end of the fourth week. Patients in both groups will have virtual follow-up visits during the intervention and 4 weeks later to be informed on the medication use and possible side effects.

Assessments of symptoms and quality of life, as well as all blood, urine, and lung tests, will be repeated at the end of the 4-week intervention. After the intervention period, a 4-week

Table 1. Schedule of enrolment, interventions, and assessments

Time point	Study period								
	Allocation		Post Allocation				Close up		
	T0	T1	T2	T3	T4	T5	T6	T7	T8
Enrollment									
Eligibility screen	*								
Inform consent	*								
Medical history and physical examination	*								
Allocation	*								
Intervention Glasthma/control		*	*	*	*				
Assessment									
Baseline survey	*								
Asthma severity	*	*	*	*	*	*			
Quality of life	*	*	*	*	*	*			
Lung function	*						*		
L:M in urine	*						*		
Blood tests	*						*		
Rate of symptom relapse							*	*	*
Health resource utilization data	*	*	*	*	*				
Safety		*	*	*	*				
Follow up							*	*	*
End line survey									*

follow-up period will follow. During these 4 weeks, patients will continue the standard treatment, with weekly recordings of symptom severity and quality of life scores, as well as the need for rescue medication.

Participants will be recruited by a pulmonologist and clinical allergist from the Respiratory Clinic at Ghaem Hospital in Mashhad. Classified online posters and advertisements will also be used to inform and engage patients. Inclusion criteria are a history of asthma over 6 months and an FEV1 of 60-80%.

Patients with one or more of the following conditions will be excluded: cognitive diseases, history of seizure disorder, use of oral or systemic corticosteroids, pregnancy or lactation, allergy to nuts, need for hospitalization for any reason, smoking, exacerbation of the disorder at the start of the study, high blood pressure or diabetes, and concurrent participation in other trials or participation in a trial in the previous month.

3. Interventions

Patients in the intervention group will be instructed to receive 7.5 mL of Glasthma syrup twice daily for 4 weeks in

combination with an inhaled corticosteroid (fluticasone) and a long-acting inhaled beta-agonist (fumarate). The daily dose of Glasthma syrup contains aqueous extract of *Cydonia oblonga* (1.5 g), licorice root (*Glycyrrhiza glabra*, 0.7 g), jujube (*Ziziphus jujuba*, 0.7 g), *Echium amoenum* (1.2 g), and hazelnut (1.5 g). The formula for this syrup has been adapted from the recommendations of Persian medicine reference books and common medical evidence. Dosages for each ingredient were determined according to previous studies [8]. Aqueous extracts were immersed in a laboratory water bath at 50°C for 6 hours. The drug has been tested for chemical and microbiological contamination in the Testa quality control laboratory. In addition, drug quality assessment was performed by measuring the polyphenol content of formulations in the Testa quality control laboratory. Participants in the control group will receive 7.5 mL of placebo syrup twice a day for 4 weeks with standard medications. Placebo syrup consists of a combination of carboxymethyl cellulose (CMC, 0.5%), Sativoside as the main sweetener (1%), and food coloring to obtain the color of Glasthma syrup.

[figure not shown]

Figure 1. Flowchart of trial procedure.

4. Randomization, allocation concealment, and blinding

Eligible patients will be randomly allocated into the intervention group or the placebo group in a ratio of 1:1. Permuted block-randomization will be used for randomization. Each block has four numbers. Sequences generated via <https://www.sealedenvelope.com> will be provided to researchers in sealed, opaque, and sequentially numbered envelopes. Project researchers will open one of the envelopes as each patient arrives at the hospital, and the patient will be assigned to the group described in the envelope. Assignment data will be kept confidential until the trial ends and the assessment is complete. Patients,

investigators, outcome assessors, and information analysts will be blinded to group assignments.

The randomization agenda and blind codes will be kept strictly confidential until the statistical evaluation is completed. Blind evaluation will be ensured by using a matching placebo syrup of the same color, shape, and taste as the intervention syrup. The quality of Glasthma syrup and matching placebo will be carefully controlled, checked, and verified by the researchers.

5. Sample size

The sample size used to evaluate the initial results needs to

be sufficient to achieve statistical and clinical significance. According to the L:M literature [29], a sample size of 5 patients was obtained: with an expected loss of 20%, 7 patients were selected. The sample size obtained based on FEV1 [30] and ACQ7 questionnaire [31] was also the same. Hence, a sample size of 7 participants in each group corresponds to a statistical power of 90%, ignoring 0.05 bilateral type I error, to detect a difference of 2.5 in this experiment with p-values less than 0.05 indicating statistical significance. We increased the sample size to 10 participants per group taking into account a 20% loss for follow-up and other potential losses related to non-compliance and quality control.

Researchers will attend a training session to prepare for their role. Each will be given a copy of the workflow and asked to commit to the protocol. The training will provide information on registration process and assessment of quality of life. PEF and blood tests and urinalysis will be performed by relevant specialists.

The data will be collected in a report file and entered into a pre-designed statistical software form. During the trial period, data will be entered and recorded twice by two different users, and any changes made on the data will be recorded and dated on the relevant forms. Two qualified people will check the quality of the data regularly. Data review and monitoring during the project will be performed by an independent supervisor other than the project sponsor or researcher. It is the responsibility of the Mashhad Medical University to monitor the data and the trial process and, if necessary, decide to terminate the study early.

RESULTS

1. Outcomes

Based on previous studies, the changes in patients' clinical symptoms and evaluation of lung function and intestinal permeability from the beginning to the end of the follow-up period were selected as the primary outcome of the research design.

The Asthma Control Questionnaire (ACQ) will also be used to assess the severity of the symptoms. The first five questions are about the symptoms of the disease. Question 6 examines the use of rescue drugs, and Question 7 examines the level of FEV1 in pre-bronchodilators. Each parameter is categorized from 0 (fully controlled) to 6 (fully uncontrolled). The minimum clinically significant difference is 0.5 [32].

Lung function test with HI-801 multifunction spirometer, change in forced expiratory volume per second (FEV1), ratio of forced vital capacity captured by forced expiratory volume per second (FEV1/FVC) before and after drug withdrawal in the intervention and placebo groups will be examined.

To determine gut permeability, we will measure the ratio of mannitol in the 5-hour urine at the beginning and end of the intervention. In this method, non-metabolized sugar molecules in the quantity of 5 grams of lactulose and 2 grams of mannitol in the form of sachet will be used and the degree of permeability or malabsorption of the intestine will be determined by the amount of secretion of these two sugars in 5-hour urine by standard LC-MS/MS (6410 LC/MS/MS triple quadrupole). The standard required amount is diluted with 10 mm ammonium acetate phase in HPLC grade water: ACN (80:20), SIL column of 25 cm, injection volume of 10 μ L, flow rate of 0.6 mL/min. The negative status for lactulose is 341.2/161 or 341.2/101.1, while that for mannitol 181.1/101 or 181.1/89. The tests will be performed in a quality control laboratory.

As the secondary outcome, the patients' quality of life will be assessed using the Asthma Short Quality of Life Questionnaire (mini-AQLQ) at the beginning and end of the intervention [33]. This questionnaire comprising 15 questions will evaluate disease symptoms, environmental effects, patients' feelings, and limitations in patients' activity. For each question, the scores vary from 0 to 6; the lower the score, the lower the quality of life. The minimum clinically significant difference is 0.5 [34].

Laboratory tests to be performed include analysis of whole blood samples, total serum IgE levels, renal and liver function tests, urinalysis, and ClCr at the start and end of the intervention. In this study, patients will be excluded from the study if any disease is observed according to the test results at the start of admission. Changes in each dose are normally recorded to assess the efficacy or possible side effects of the drug.

In addition, other conditions, such as the need for hospitalization or emergency treatment and use of rescue medication, will also be recorded. If we notice symptoms of other diseases during the intervention, or if a patient requires an unforeseen medication, the patient will be excluded from the study, and the results will be recorded.

2. Safety assessment

Liver and kidney function tests will be performed using blood and urine samples at the beginning and end of the inter-

vention. During the intervention, researchers will also follow up with patients, and any signs, symptoms, and unexpected feelings will be recorded, reported, and linked to the experimental drug.

Results, severity, time of onset, duration, duration of treatment, and follow-up of side effects will be recorded in the report form. All side effects will be assessed to examine the causal impact of the intervention according to the criteria established by the Iranian National Biomedical Research Ethics Committee.

Participants will be excluded from the study if they experience intolerable side effects, acute or persistent organic disease, new-onset disease, a need to take non-asthma medication, or patient dissatisfaction during the study period. The patients' withdrawal from the plan will be recorded stating the reasons for discontinuing the drug and the final date of its use.

Deleted and terminated projects will be analyzed in the final report. Withdrawal of the patient without any reason is acceptable and will not interfere with the continuation of the daily treatment of the patient.

The researchers will explain the results of the clinical and laboratory tests to the patients. Participants will be provided with ongoing support throughout the study, including free registration, medical consultation, and follow-up.

3. Statistical analysis

Data analysis will be performed by independent statistical experts using IBM Statistics 16.0 software. Quantitative data will be expressed as mean and standard deviation, or median and quadratic range. Dual data, such as symptom recurrence, will be shown as 95% hazard ratios and confidence intervals. A p-value less than 0.05 will be considered to indicate a statistically significant difference.

Basic characteristics will be described using standard statistical analysis methods. Continuous variables will be analyzed using t-tests, while classified variables will be analyzed using chi-square tests. The main analysis will include the treatment intent and the subject of each protocol for initial results. The latter prospective approach will be used in an intention-to-treat analysis to assign missing data.

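### Table 1 and the follow-up text disagree on whether symptoms, quality of life and rescue use are recorded in follow-up, on which the relapse and end-of-follow-up symptom outcomes depend

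*Protocol*

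**What the plan says.** The Protocol, Materials and Methods, 2. Trial procedure, sets treatment in weeks 1 to 4 and follow-up in weeks 5 to 8. For follow-up, it has patients stay on standard treatment "with weekly recordings of symptom severity and quality of life scores, as well as the need for rescue medication".

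Table 1, in the same section, gives these marks:
- "Asthma severity": T0 to T5.
- "Quality of life": T0 to T5.
- "Rate of symptom relapse": T6, T7 and T8.
- "Health resource utilization data": T0 to T4.
- Rescue medication: no row.

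Results, 1. Outcomes, defines the primary outcome over a window that reaches the end of follow-up: changes in symptoms, lung function and permeability "from the beginning to the end of the follow-up period were selected as the primary outcome". The same section says that quality of life "will be assessed using the Asthma Short Quality of Life Questionnaire (mini-AQLQ) at the beginning and end of the intervention". Symptom recurrence is a secondary outcome in the abstract. It is to be summarised with a hazard ratio in Results, 3. Statistical analysis, and the Discussion presents it as a main reason for having the follow-up period.

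**The concern.** The assessment schedule and the narrative are both current text, and they cannot both be followed in weeks 5 to 8. Staff usually work from the schedule table. If they did so here, the symptom questionnaire would stop at T5 and relapse would be judged at T6, T7 and T8 with no symptom score taken at the same contact.

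Two outcomes depend on which version is used. The symptom part of the primary outcome needs a score at the end of follow-up. Recurrence needs repeated symptom or rescue information across follow-up if it is to be reported as a time-to-event comparison. With 10 patients per group there is little room to lose scores, and an analysis plan cannot recover questionnaires that were never given.

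**Working it through.** No formula applies. The check is to list the marked cells of Table 1 and set them beside the text. Each assessment row checked has nine cells, T0 to T8.

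| Item | Table 1 | Text |
|---|---|---|
| Syrup | T1–T4 | weeks 1–4 |
| Symptom severity | T0–T5 | weekly in treatment and weekly in weeks 5–8 |
| Quality of life | T0–T5 | weekly in both periods (Trial procedure); start and end of intervention (Outcomes) |
| Rescue medication | no row | weekly in weeks 5–8; also item 6 of the ACQ, and recorded with no stop date (Outcomes) |
| Relapse | T6–T8 | assessed over the four follow-up weeks |
| Lung function, L:M, blood tests | T0, T6 | start and end of the 4-week intervention |
| End-line survey | T8 | content not described |

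**Step 1: overlap of symptom score and relapse.** Severity is marked at {T0, T1, T2, T3, T4, T5} and relapse at {T6, T7, T8}. The intersection is empty, so 0 of 3 relapse points carry a symptom score. This does not depend on what the T labels mean.

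**Step 2: end of follow-up.** The last severity mark is T5 and the last column is T8. Under the table, no symptom score is scheduled at the end of the window that defines the primary outcome.

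**Step 3: can a choice of weeks for the T labels remove the conflict?** The protocol does not define them, so each reading below is an assumption.
- *T1–T4 are weeks 1–4 and T5–T8 are weeks 5–8.* The table then gives 1 of the 4 weekly follow-up symptom scores that the text promises (T5). The lung, L:M and blood tests fall in week 6, not at the end of treatment.
- *T5 is the end-of-week-4 visit and later columns are weekly.* The table gives 0 of 4 follow-up scores, T6–T8 are weeks 5–7, and week 8 has no column. The tests fall in week 5.
- *T6 is the end-of-intervention visit.* The tests now fit, but relapse is marked at a visit that closes treatment. Only T7 and T8 remain for four follow-up weeks, and the table gives 0 of 4 follow-up scores.

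None of these readings yields four weekly follow-up scores, and each leaves some other part of the table at odds with the text.

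**The case against.** The strongest reply is that the measurement exists. The narrative schedules symptom, quality-of-life and rescue recordings every week of follow-up, and data are lost only if someone follows the table against it. That stands. A reader might infer from Table 1 that relapse and the end-of-follow-up symptom outcome have no measurement behind them; the narrative rules that out.

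A reader might also infer that one of the four follow-up weeks goes unobserved, because the relapse row has only three marks, and might go on to estimate a share of relapses missed. The documents do not support this. The T labels are undefined. If T5 is week 5, that week lacks a relapse mark but does carry a symptom score. The protocol gives no relapse rate from which to compute a share.

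Three smaller replies also have force:
- The health-resource row is not stated to hold rescue use, so its stop at T4 does not show that rescue recording stops there. The accurate statement is that Table 1 has no rescue row.
- The end-line survey at T8 might include symptoms. Its content is not given, and a single point would not serve T6 and T7.
- The mini-AQLQ sentence in Outcomes may name the time points to be analysed, which is compatible with weekly recording. The statistical section likewise compares quality of life at the start with the end of the intervention. That reading is reasonable, but the protocol does not state it.

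The column positions come from extracted text, so a shifted mark is possible. However, the rows are complete, and severity and quality of life show the same pattern.

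**Conclusion.** The point holds as an internal contradiction that should be corrected. Table 1 and the follow-up text give incompatible schedules for symptom severity and quality of life in weeks 5 to 8, and the table omits the rescue recording that the text promises. If the table is followed, 0 of 3 relapse points have a symptom score, and neither the primary symptom change nor recurrence has a scheduled score after T5. If the text is followed, both have weekly data. The 0 of 3 count needs no assumption beyond the table being extracted correctly. Statements about particular weeks depend on an undefined labelling, so no number of lost weeks or lost relapses can be given.

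**What to change.** 1. Define T0 to T8 in study weeks. Add columns if nine are too few for baseline, weeks 1 to 8 and the end-of-intervention visit.
2. Extend the asthma severity and quality-of-life rows to each weekly recording in weeks 5 to 8, and add a rescue-medication row over the same weeks, as the text already commits.
3. Make the relapse row cover the same weekly contacts.
4. Reconcile the lung, L:M and blood-test marks at T6 with the end-of-intervention timing in the text.
5. Reconcile the mini-AQLQ sentence in Outcomes with weekly recording, for example by saying that baseline and end of intervention are its analysis time points.
6. The Recruitment section expected the last follow-up on 23-04-2022, before the protocol was accepted on July 28, 2022. If collection is complete, state which schedule was actually followed.

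The cost is a corrected table and one edited sentence. Patients do nothing that the text does not already ask of them. Extending health-resource collection into follow-up, or fixing the rule by which relapse is scored, would go beyond what the text commits to and is not part of this correction.

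### The sample-size chain from 5 to 7 to 10 per group attaches 90% power to a loss-inflated number and then names the 20% loss again, so the stated power is not tied to one evaluable sample size

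*Protocol*

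**What the plan says.** All the statements are in the Protocol, Materials and Methods, section 5 (Sample size).

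- Starting from literature on the lactulose/mannitol ratio, "a sample size of 5 patients was obtained: with an expected loss of 20%, 7 patients were selected". The size from FEV1 and from ACQ7 is said to be the same.
- The conclusion drawn is that "a sample size of 7 participants in each group corresponds to a statistical power of 90" per cent, "ignoring 0.05 bilateral type I error", "to detect a difference of 2.5 in this experiment". No SD is given, and the 2.5 is not linked to an endpoint or a unit.
- The last step is "We increased the sample size to 10 participants per group taking into account a 20% loss for follow-up and other potential losses", which the sentence attributes to non-compliance and quality control. These other losses carry no figure.

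The abstract gives the resulting total of 20 patients, in two equal groups.

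**The concern.** A sample-size statement should run in one direction: the evaluable number that gives the target power, then the allowance for loss, then the number to randomise. Here the order is mixed. The number that comes out of the calculation is 5. The number that carries the 90% is 7, which was reached by adding the loss. The same 20% then appears a second time as a reason to go from 7 to 10.

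This is the Protocol's only power statement, and it is used to justify 20 patients for three primary outcomes. The sections on outcomes and safety list several reasons for removing patients after enrolment, so the evaluable number is likely to differ from the enrolled number. A reader needs to know which of the two the 90% refers to, and the text does not say.

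**Working it through.** **Inputs from the Sample size section:** calculated size 5; expected loss 20%; 90% power attached to 7 per group; two-sided alpha 0.05; difference 2.5 with no SD; final size 10 per group. The text does not say whether the 5 is per group or in total. I take it as per group, because the 7 derived from it is later given per group.

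**1. The loss steps.** Formula: enrolled n = evaluable n / (1 − loss), rounded up.

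- 5 / 0.8 = 6.25, so 7. This reproduces the Protocol's 7 and confirms that it already contains the 20% loss. (Multiplying by 1.2 would give 6, not 7.)
- 7 / 0.8 = 8.75, so 9. The second 20% takes 7 to 9. The step from 9 to 10 is left for the other losses.
- 10 × 0.8 = 8 evaluable per group after a 20% loss.

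**2. Can 5 and 7 evaluable both be the 90% size?** The 90% cannot be reproduced, because there is no SD. It can only be examined under an assumption about which number carries it. For a two-sample t-test with n per group and standardised effect d, the power is the probability that a noncentral t variable with 2n − 2 degrees of freedom and noncentrality d√(n/2) exceeds the two-sided 5% critical value in absolute size. I solved d for exactly 90% at n = 5, then for exactly 90% at n = 7, and read off the power at the other sizes.

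| Evaluable per group | If 5 give 90% (d = 2.35) | If 7 give 90% (d = 1.89) |
|---|---|---|
| 5 | 90.0% | 74.5% |
| 7 | 98.0% | 90.0% |
| 8 | 99.2% | 93.9% |
| 10 | 99.9% | 97.9% |

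The normal approximation gives a similar picture: 97.0% at 7 and 98.4% at 8 in the first column, 78.2% at 5 and 93.4% at 8 in the second. No single effect size puts 90% at both 5 and 7 evaluable. The two values of d are solved backwards from n. They come from no endpoint and serve only to show the conflict.

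**3. Does the stated 2.5 settle it?** Only under a further assumption. If 2.5 is read as a standardised effect (SD = 1), the t-test has 83.6% power at 4 per group, 93.2% at 5 and 99.0% at 7. The smallest size reaching 90% is then 5, which would make 5 the evaluable number. If 2.5 is a raw difference, the SD that gives exactly 90% is 2.5 / 2.35 = 1.06 for 5 per group and 2.5 / 1.89 = 1.32 for 7 per group. The Protocol does not say which applies.

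**4. The two readings of 7.**

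- *7 evaluable.* The 90% belongs to 7, and the 5 reported as the result of the calculation is not the 90% size; or it belongs to 5, and the power at 7 is higher than stated. One of the two statements has to change.
- *7 enrolled.* After a 20% loss, 7 × 0.8 = 5.6, so at least 5 remain and the 90% can stand. The 20% has then been used already, and naming it again on the way to 10 is a repeat.

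**The case against.** The strongest reply is that the text is loose rather than wrong, and that the looseness does no harm. Three parts of it stand.

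- The last step does not rest on the 20% alone. It also names non-compliance and quality-control losses, and these can account for the tenth patient. A reader might infer from 7 / 0.8 giving 9 that 10 is an arithmetic error. The full sentence does not support that.
- The 7 may mean 7 enrolled. A reader might infer that the 90% is wrong whichever way the text is read. It is not: on the enrolled reading the label can stand and only the repeated 20% remains.
- The double count makes the trial larger. A reader might infer that the trial is too small for its stated power. This point does not show that. Ten per group less 20% leaves 8, above both 5 and 7, and on the more demanding assumption, that 7 evaluable are needed, 3 of 10 patients per group can be lost before the number falls below 7.

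It might also be said that such detail can wait for the statistical analysis plan. That does not help here, because the Protocol states the calculation itself and states it inconsistently. What remains is that the other losses do not explain why the 20% appears twice, and that on either reading of 7 one sentence has to be corrected.

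**Conclusion.** The point holds as an inconsistency in the stated calculation. Either the 90% is attached to the wrong number (7 read as evaluable) or the 20% loss is counted twice (7 read as enrolled).

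The size of the error depends on an assumption that the Protocol does not settle. If 5 evaluable give 90%, the stated figure for 7 is about 8 points too low (98.0 − 90.0). If 7 evaluable give 90%, the 5 reported as the calculated size would give about 15.5 points less than 90% (90.0 − 74.5). Both figures assume a two-sample t-test with equal groups and an effect solved to give exactly 90%; neither is an estimate of the trial's true power.

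At about 8 evaluable per group the power is about 94% or 99% under these two assumptions, so the planned 20 patients are not called into question by this point. Whether the 2.5 is a sound target cannot be judged without its endpoint and SD.

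**What to change.** Restate the calculation in the Sample size section as one chain:

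1. Give the evaluable number per group that yields 90% power at two-sided 0.05, with the endpoint, the difference and the SD that the authors used. Say which endpoint and unit the 2.5 belongs to.
2. Apply the 20% loss once: 5 becomes 7, or 7 becomes 9, depending on which is the evaluable number.
3. Describe the remaining patients up to 10 per group (3 in the first case, 1 in the second) as the allowance for non-compliance and quality-control losses.
4. State the power at the roughly 8 evaluable per group expected after a 20% loss.

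The SDs and standardised effects in the check above should not be copied into the Protocol. They are solved from the sample sizes, and only the authors' own inputs can replace them.

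The cost is two or three sentences and a look at the original calculation. The 20 patients stay unchanged.
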